13.13 Use and Publication of Study Results

All unpublished documentation (including the protocol andCRF) given to the Investigator is strictly confidential. All recipients must agree not to disclose the information herein contained to any person without the prior written authorization of Anika Therapeutics, Inc. The submission of these documents to the regulatory authorities is expressly permitted. The Investigator agrees that Anika Therapeutics, Inc. maintains the right to use the results of this study in their original form and/or in a global report for submission to governmental and regulatory authorities of any country.

The results of the study may be presented during scientific symposia or published in a scientific journal only after review by Anika Therapeutics, Inc. in accordance with executed study contract.

13.14 Pre-Study Documentation

The Investigator must provide the following documents prior to the enrollment of any subjects as appropriate to local country regulation:

- Signed and dated protocol signature page by the Principal Investigator (Investigator) and all Sub-Investigators.
- Signed and dated protocol amendment(s) signature page by the Investigator and all Sub-Investigators, when applicable.

- Current curriculum vitae (CV) for the Investigator and all Sub-Investigators
- Current medical license for the Principal Investigator and all Sub-Investigators (if applicable).
- Financial disclosure statements signed and dated by the Investigator and all Sub-Investigator as required.
- Copy of the EC approval letter for the protocol and any other pertinent documents.
- List of EC committee members.
- Copy of the EC-approved ICF to be used.
- Fully executed Clinical Trial Agreement.
- Delegation of Authority form.
- Certified translations of EC approval letters, and approved ICF document (when applicable).
- Insurance certificate as required.

13.15 Investigator Responsibilities

- The Investigator should be qualified by education, training, and experience to assume responsibility for the proper conduct of the clinical study.
- The Investigator must have knowledge on the use, application, implementation or administration of Cingal and the requirements for clinical, efficacy and safety follow-up.
- The Investigator should be familiar with and trained on the appropriate use of Cingal as described in the protocol and in the current Instructions for Use.
- The Investigator is responsible to ensure that the Cingal is administered only by trained personnel in accordance with the protocol and instructions for use.
- The Investigator should disclose any potential conflicts of interest, including financial, that interfere with the conduct of the clinical investigation or interpretation of the results.
- The Investigator should be trained on and comply with GCP regulations and the applicable regulatory requirements.
- The Investigator should demonstrate that the proposed Clinical Trial Site has the following:
 - One or more qualified Investigators;
 - Qualified site staff;
 - Adequate facilities for the foreseen duration of the clinical study;

- Required number of eligible subjects needed within the agreed recruitment period.
- The Investigator must create and maintain source documentation throughout the clinical study and make it available as requested during monitoring visits and audits.
- The Investigator should permit monitoring and auditing by the Sponsor or Sponsor's designee and inspection by the appropriate regulatory authorities. Investigator should be accessible (when possible) to the monitor to respond to questions.
- The Investigator should have sufficient time to conduct and oversee the trial.
- The Investigator should ensure the EC has the most up to date study related documentation (e.g. Instructions for Use Protocol).
- The Investigator should inform the subject's primary physician about the subject's participation in the trial if permitted to do so by the subject.
- The Investigator will provide the Sponsor with copies of any clinical-investigation-related communications between the Investigator and the EC.
- The Investigator must be aware of the AE and adverse reaction reporting process, including reactions related to application of the Cingal.
- The Investigator shall ensure accuracy, completeness legibility and timeliness of the data reported to the Sponsor in the eCRFs and in all required reports.
- The Investigator must have knowledge of the risk analysis of the Cingal, knowledge of the
 requirements for storage, handling, administration, and destruction or disposal of the Cingal
 including any hazard to those handling the product and close contacts and the risk to the
 environment.
- The Investigator must ensure that the particular requirements for the application of the CINGAL, such as standardization of injection procedures if possible and training of the healthcare professionals involved, are communicated to the site staff including the physicians or other specialists involved.
- The Investigator shall ensure maintenance and calibration of the equipment relevant for the assessment of the clinical study is appropriately performed and documented, when applicable.
- The Investigator must be knowledgeable with the method of obtaining informed consent.

- The Investigator shall ensure and document appropriate training if any authorized designee is appointed to conduct the informed consent process.
- The Investigator must inform the trial subject of the particular issues that arise for the Cingal. In particular, both the ICF and any other written information to be provided to the subjects should include an explanation of the following:
 - o Provisions for subject data protection and confidentiality;
 - The arrangements for follow-up before and after the end of the trial, including after subjects withdraw from the study and including the information to be provided to the subject for use in the event of problems arising after the end of the trial;
 - The length of follow-up;
 - The definition of the end of the trial and its relationship to the follow-up after the end of the trial;
 - The need to keep an accurate subject diary;
- The Investigator shall provide adequate medical care to a subject during and after subject's participation in a clinical study in the case of AEs.
- The Investigator shall ensure that clinical records are clearly marked to indicate that the subject is enrolled in a particular clinical study.
- The Investigator must provide the subject with the following:
 - Information on any new significant findings occurring during the clinical study, including the need for additional medical care that may be required;
 - Well-defined procedures for possible emergency situations to the clinical study and make arrangements for emergency treatment,
 - Some means of showing the subjects participation in the clinical study, together with identification and compliance information for the concomitant treatment measures (If appropriate).

13.16 Sponsor's Responsibilities

• Anika Therapeutics, Inc. may delegate some of the responsibilities to a CRO but will maintain oversight of the clinical study. Anika shall define, establish and allocate all the roles and responsibilities related to the clinical study in one or more written agreements.

- Anika Therapeutics, Inc. shall implement and maintain written clinical quality procedures to ensure that the clinical study is designed, conducted and monitored, and that data are generated, documented, recorded and reported in compliance with EN ISO 14155:2011 and ICH E6, this protocol, any subsequent amendments, and any other applicable standards and regulatory requirements.
- Anika Therapeutics, Inc. will ensure that there is written agreement with the Investigator/institution and any other parties involved with the clinical study.
- Anika Therapeutics, Inc. will designate appropriately qualified medical personnel to advise on medical questions or problems.
- Anika Therapeutics Inc. will utilize appropriately qualified individuals to supervise the overall
 conduct of the trial, to handle the data, to verify the data, to conduct the statistical analyses,
 and to prepare the trial reports.
- Anika Therapeutics, Inc. will select Investigators/institutions that are qualified by training and
 experience with adequate resources to properly conduct this trial for which the Investigator
 is selected. Anika will also select a coordinating Investigator, if appropriate. Anika
 Therapeutics, Inc. will ensure members of the site staff and their designated authorization(s)
 are identified in a log with details.
- Anika Therapeutics, Inc. will ensure that all Investigators and all other parties involved are given instructions on uniformly assessing and documenting clinical and laboratory findings.
- Anika Therapeutics Inc. will establish the particular requirements for the application of the CINGAL, and train the Investigator in the requirements for storage, handling, administration, and destruction or disposal of the CINGAL including hazards to those handling the product and close contacts and the risk to the environment.
- Anika Therapeutics, Inc. will designate or appoint one or more monitors, or otherwise assume the responsibilities of the monitor(s) and ensure documentation of training, experience and scientific or clinical knowledge for all the relevant parties involved in order to adequately conduct the clinical study. This includes training on the following:
 - Use of the Cingal
 - o Investigator's Brochure
 - o **Protoco**l
 - eCRFs and instructions for completion

Anika Therapeutics, Inc. Cingal 20-03

 The written ICF and informed consent process as well as other written information provided to subjects

- Sponsor's written procedures; EN ISO 14155:2011; and any other applicable regulatory procedures.
- Anika Therapeutics, Inc. will receive disclosures of conflicts of interest from PIs and Investigators.
- Anika Therapeutics, Inc. will assure the accuracy of any translations, as applicable.
- Anika Therapeutics, Inc. will ensure that any electronic trial data handling and/or remote electronic trial data systems, are validated with the following characteristics:
 - Data changes are allowed with an audit trail;
 - o System is secure and does not allow for unauthorized access to the data;
 - A list of the individuals who are authorized to make data changes is maintained;
 - Adequate backup of the data is maintained;
 - An unambiguous subject ID is used to allow identification of all the data reported for each subject.
- Anika Therapeutics, Inc. will ensure maintenance of sponsor-specific essential documents
 pertaining to the trial in conformance with the applicable regulatory requirement(s) of the
 country(ies) where the product is approved, and/or where the sponsor intends to apply for
 approval(s).
- Anika Therapeutics, Inc. will inform the Investigator/institution in writing of the need for record retention and will notify the Investigator/institution in writing when the trial related records are no longer needed.
- Anika Therapeutics, Inc. will provide insurance or indemnify the Investigator/institution against claims arising from the trial, except for claims that arise from malpractice and/or negligence.
- Anika Therapeutics, Inc. will obtain the following information documentation from each participating EC:
 - The name and address of the EC.
 - A statement obtained from the EC that it is organized and operates according to GCP and the applicable laws and regulations.

- Documented EC approval/favorable opinion for the protocol and any subsequent amendments (as applicable) and re-approvals.
- Anika Therapeutics, Inc. will update the Investigator's Brochure as significant new information becomes available.
- Anika Therapeutics, Inc. or designee will verify that each subject has consented, in writing, to direct access to his/her original medical records for trial-related monitoring, audit, EC review, and regulatory inspection.
- Anika Therapeutics, Inc. is responsible for the ongoing safety evaluation of the Cingal trial.
- Anika Therapeutics, Inc. will notify all concerned Investigators/institutions and the regulatory authority(ies) of findings that could affect adversely the safety of subjects, impact the conduct of the trial, or alter the EC approval/favorable opinion to continue the trial.
- Anika Therapeutics, Inc. will submit any required application(s) to the appropriate authority(ies) for review, acceptance, and/or permission (as required by the applicable regulatory requirement(s)) to begin the trial(s).
- Anika Therapeutics, Inc. will ensure that all required EC, or other regulatory approvals are obtained and documented; and that appropriate provisions are made to meet any specific conditions imposed by the EC. Anika will ensure that any modification(s) required by the EC or other regulatory authority are made and documented by the PI and have gained the approval of the EC or other regulatory authority.
- Anika Therapeutics, Inc. will expedite the reporting to all concerned Investigator(s)/institutions(s), to the EC, where required, and to the regulatory authority(ies) of all ADEs that are both serious and unexpected, where required.
- Anika Therapeutics, Inc. will submit to the regulatory authority(ies) all safety updates and periodic reports, as required by applicable regulatory requirement(s).
- Anika Therapeutics, Inc. will ensure that an ongoing risk analysis, based on existing knowledge of the type of product and its intended use, is performed and provided to the Investigator involved in a clinical study with the CINGAL, through the Investigator's Brochure or updates to it and to the subject through the ICF or updates to it.
- Anika Therapeutics, Inc. will also incorporate the risk analysis and risk management plan of Cingal and share this with the Investigators;
- Anika Therapeutics, Inc. or designee shall be responsible for:

- Documenting correspondence with all parties involved in the clinical study, including the EC and regulatory authorities;
- Ensuring that the clinical study is appropriately monitored by determining the extent and nature of the monitoring;
- Reviewing the monitoring reports and follow-up on actions required in the monitoring report;
- o Taking prompt action to secure compliance with all clinical study requirements;
- Submitting progress reports, including safety summary deviations, when requested, to all reviewing EC's and the regulatory authorities.

Appendix 1 Patient Global Assessment

To be assessed by the Subject as the first questionnaire.

The pain the subject felt in INDEX ankle caused by osteoarthritis during the last 24 hours.

Have the Subject record their response with an "X":

Think about the pain you felt in your STUDY ankle caused by your osteoarthritis during the last 24 hours.

"Considering all the ways the osteoarthritis in your STUDY ankle affects you, what is your assessment of how much your STUDY ankle is bothering you today?"

0	1	2	3	4	5	6	7	8	9	10
No Pain		Mild			Moderate	,		Severe	1	Worst Pain

Appendix 1: Numerical Pain Scale NRS on Walking for Joint Pain

INSTRUCTIONS

- 1. Place an "X" in the box below that indicates the amount of pain the subject feels in joint on walking on a flat surface in the last 24 hours.
- 2. Complete for the following joints:

					INDEX					
					HIP					
0	1	2	3	4	5	6	7	8	9	10
No Pain										Worst Pain
				96	KNEE					
					XILL					
	4		0				-			40
0	1	2	3	4	5	6	7	8	9	10
No Pain	Mild Moderate Severe							Worst Pain		
					ANKLE					
		1			AIIIILL					
0	1	2	3	4	5	6	7	8	9	10
No Pain	Mild				Moderate			Severe		Worst Pain

CONTRALATERAL

HIP

0	1	2	3	4	5	6	7	8	9	10
No Pain		Mild			Moderate	9		Severe		Worst Pain

KNEE

0	1	2	3	4	5	6	7	8	9	10
No Pain		Mild	1.		Moderate			Severe	1.	Worst Pain

ANKLE

0	1	2	3	4	5	6	7	8	9	10
No Pain		Mild			Moderate			Severe		Worst Pain

Appendix 3 American Orthopedic Foot and Ankle Score AOFAS Ankle-Hindfoot Scale (100points Total)

I Pain (40 points)

None	40
Mild, occasional	30
Moderate, daily	20
Severe, almost always present	0

II Function (50 points)

ctivity limitations, support requirement	
No limitations, no support	10
No limitation of daily activities, limitation of recreational activities, no support	7
Limited daily and recreational activities, cane	4
Severe limitation of daily and recreational activities, walker, crutches, wheelchair, brace	0

faximum walking distance, blocks	
Greater than 6	5
4-6	4
1-3	2
Less than 1	0

Walking surfaces	
No difficulty on any surface	5
Some difficulty on uneven terrain, stairs, inclines, ladders	3
Severe difficulty on uneven terrain, tairs, inclines, ladders	0

Gait abnormality	
None, slight	
Obvious	4
Markeo	0

Sagittal motion (flexion plus extension)	
Normal or mild restriction (30° or more)	8
Moderate restriction (15°-29°)	4
Severe restriction (less than 150)	0

Hindfoot motion (inversion plus eversion)	
Normal or mild restriction (75%-100% normal)	6
Moderate restriction (25%-74% normal)	3
Marked restriction (less than 25% normal)	O

Ankle-hindfoot stability (anteroposterior, varus-valgus)	
Stable	8
Definitely unstable	0

II Alignment (10 points)

Good, plantigrade foot, midfoot well aligned	15
Fair, plantigrade foot, some degree of midfoot malalignment observed, no symptoms	8
Poor, nonplantigrade foot, severe malalignment , symptoms	0

Total=100

American Orthopaedic Foot and Ankle Society

From: http://www.aofas.org/i4a/pages/index.cfm?pageid=3494

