6. ENDPOINTS

6.1 Primary Endpoint:

 Reduction of index ankle Numerical Rating Scale (NRS) pain on walking from baseline to 6 Months post injection.

6.2 Secondary Endpoints:

- Improvement in AOFAS index ankle from baseline to 6 months post injection.
- Improvement in Patient Global Assessment (PGA) from baseline to 6 months post injection.
- OMERACT-OARSI in the index ankle responder rate at 6 months post injection.
- Time to treatment failure
- Reduction in Medication usage from baseline to 6 months post injection.

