7. STUDY PROCEDURES

7.1 Schedule of Events

Assessments	Screening Visit	Baseline Visit	Month 1 Visit	Month 3 Visit	Month 6 Visit
Assessments	Day -14 to -7 ±2 days	Day 0	±3 days	± 7 days	± 7 days
Informed Consent	Х				
Evaluation of Enrollment Criteria	х	х			
Demographics	Х				
Vital Signs	Х				
History Joint OA (Index & Contralateral for hip, knee and ankle)	х				
Medical History	Х				
Concomitant Medication	х	Х	X	Х	х
Assess non-drug therapies	Х	Х	X	Х	х
Adverse Event Assessment		Х	X	Х	х
Collect & Review Subject Diary		Х	Х	Х	х
Rescue Medication usage / washout		Х	Х	Х	х
Patient Global Assessment (PGA)	х	Х	Х	Х	х
AOFAS index for index and contralateral ankle	х	х	Х	х	Х
Index and Contralateral Joints Pain (0-10 Numeric Rating Scale) for Hip, Knee and Ankle joints	х	х	Х	х	х
Physical Evaluation of Index and Contralateral Joints for Hip, Knee and Ankle joints	х	х	Х	х	х
Study Injection		Х			
Dispense Subject Diary	x	х	X	X	

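### As extracted, the AOFAS form in Appendix 3 heads alignment at 10 points but scores its rows 15/8/0, so its maximum exceeds the stated 100

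*Protocol*

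**What the plan says.** Protocol Appendix 3 reproduces the scoring form. Its title reads "Ankle-Hindfoot Scale (100points Total", and its last line repeats a total of 100. The sections are pain at 40 points, "II Function (50 points" and "II Alignment (10 points". Under alignment, the row "Good, plantigrade foot, midfoot well aligned" carries 15, the row "Fair, plantigrade foot, some degree of midfoot malalignment observed, no symptoms" carries 8, and the poor row carries 0. Under "Gait abnormality" the score for the best row is not legible in the extracted text; the next row down carries 4.

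Protocol 6.2 lists as a secondary endpoint "Improvement in AOFAS index ankle from baseline to 6 months post injection". The Schedule of Events in 7.1 has "AOFAS index for index and contralateral ankle" at all five visits. SAP 4.1.3.2 tests the AOFAS change with a one-sample t-test and tables it in the primary-endpoint layout of 4.1.2.1, where baseline and visit results stand beside the change. No other section gives a rule for scoring alignment, and the revision history records no change to Appendix 3.

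SAP 4.1.3.2 (AOFAS) and 4.1.3.3 (PGA) both describe the tested difference as one between elbow pain scores. Both state the alternative as a mean change above zero.

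**The concern.** The heading and the rows of one section give different maxima, 10 and 15. The form cannot total 100 as it states if its rows are used as printed. Anyone who scores from this page could record totals above 100 and give alignment more weight than its heading allows. Because the SAP tables AOFAS levels as well as changes, an error in the rows would show in the reported baseline and visit means even where it cancels in the change.

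A smaller matter lies in the SAP text for the same endpoint. The variable named in the test is not the AOFAS or the PGA, and one direction of change is written for scales that run in opposite directions. AOFAS rises with improvement, while PGA and NRS fall.

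**Working it through.** **Inputs, all from Appendix 3.** Pain, best row: 40. Function, legible best rows: activity 10, walking distance 5, walking surfaces 5, sagittal motion 8, hindfoot motion 6, stability 8. Gait, best row: not legible; the row below it is 4. Alignment rows: 15, 8, 0. Headings: 40, 50, 10. Stated total: 100.

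**The plan's own figure from its headings.** 40 + 50 + 10 = 100. The stated total is reproduced.

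**The same figure from the rows.**
- Function without gait: 10 + 5 + 5 + 8 + 6 + 8 = 42.
- Gait implied by the Function heading: 50 − 42 = 8.
- Row maximum with gait 8: 40 + 50 + 15 = 105.
- Lower bound: the best gait row cannot score below the 4 printed beneath it, so the maximum is at least 40 + 42 + 4 + 15 = 101.
- Gait score needed for 100 with alignment at 15: 100 − 40 − 42 − 15 = 3. This is below the row beneath it and would leave Function at 45, so it is not admissible.
- With alignment at 10 and gait at 8: 40 + 50 + 10 = 100.

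**Effect on levels, if 15/8/0 is used.** Each good rating is 15 − 10 = 5 points above the section maximum. The excess in a mean level is 5 × (share rated good), plus a term for fair ratings that cannot be computed because the documents do not show whether 8 is right. If 8 is right, that term is zero and the excess is 2.5 points at a 50% share, 4.0 at 80% and 5.0 at 100%. These shares are assumptions; the documents give none.

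**Effect on change.** With no change of category, the excess cancels. A poor-to-good shift counts 15 instead of at most 10, an excess of 5. Over 25 subjects, one such shift adds 5 / 25 = 0.2 to the mean.

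**Why all three rows need checking.** As printed, the good-to-fair step is 15 − 8 = 7. If only the top row were changed to 10, it would become 10 − 8 = 2, beside a fair-to-poor step of 8.

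**Scorings that enter the endpoint.** The endpoint uses the index ankle, and baseline is normally the last pre-treatment observation (Protocol 9.2, SAP 4.2). Baseline and Month 6 give 25 × 2 = 50 scorings; with Months 1 and 3, 25 × 4 = 100.

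**Direction in the SAP.** If change is taken as visit minus baseline throughout, improvement is positive for AOFAS but negative for PGA and NRS. A single order of subtraction cannot match a positive alternative on all three.

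**The case against.** The strongest reply is that the page is visibly damaged. Letters are missing from several labels, a letter O stands for a zero, a degree sign has become a digit, and the best gait score is lost from the same column of numbers. A misread 15 is possible, and a broken table is not an error in the plan. This stands as a reason to check the form before changing anything. It does not dispose of the point: 15, 8 and 0 form a coherent descending set, while the 10-point heading agrees with the other headings and with both statements of the total.

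The second reply is that scores come from the CRF, which is not among the documents. A reader might infer that subjects have been mis-scored. The documents do not support that; they show only what the appendix prints.

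The third reply is that the endpoint is a change score, so a constant excess cancels. This also stands. A reader might infer a 5-point bias in the AOFAS endpoint, or count every scoring of both ankles at all five visits as affected. Neither follows. The excess enters the change only when a category shifts, and contralateral and screening scores do not normally enter the index-ankle change from baseline.

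On the SAP wording, the section titles identify the intended variables, and the endpoint names (reduction for NRS, improvement for AOFAS and PGA) show that benefit is meant. The order of subtraction is still not stated.

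**Conclusion.** The point holds, as a minor one, for the text as extracted. The alignment heading and the stated total conflict with the alignment rows, and no admissible gait score or other section resolves the conflict. The row maximum is 105 with the implied gait score of 8 and at least 101 otherwise, against a stated 100.

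The consequence is conditional on 15/8/0 having been used for scoring. In that case the tabled AOFAS levels at baseline and each visit are too high, and totals above the scale's own maximum can occur. The change endpoint moves only with shifts in alignment category, by 0.2 for one poor-to-good shift if all 25 subjects contribute; the documents give no reason to expect many. The primary NRS endpoint does not use this form and is unaffected by the discrepancy.

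The SAP wording is a text correction to make at the same time and does not raise the severity.

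**What to change.** 1. Confirm the printed alignment values, and the best gait score, on the form as issued.
2. Reconcile all three alignment rows, including the middle one, with the 10-point heading and the 100-point total, using the source instrument.
3. Check which values the CRF and the scoring program apply. If 15/8/0 was applied, rescore from the recorded alignment categories; otherwise correct the appendix only.
4. In SAP 4.1.3.2 and 4.1.3.3, replace the elbow pain score with the AOFAS total score and the PGA score. Define change so that a positive value means improvement on each scale: visit minus baseline for AOFAS, baseline minus visit for PGA and NRS.

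The cost is a correction to the appendix and SAP text and one check of the CRF and program. No new data are needed, because any rescoring uses categories already collected.
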